8. HANDLING OF MISSING VALUES

Every effort will be made to collect all vomiting-related information. In the ED, patients will be under observation, complete efficacy data is expected. Rare cases may occur in which a patient leaves the ED before any observations can be made. In addition, some patients may not report events between the time they leave the ED and 24 hours after first dose of study medication. It is expected that >90% of patients will provide data until at least 24 hours after initial dosing. Patients who drop out of the study and patients who have unknown primary endpoint will be imputed as failures/non-responders for the primary analysis.

Diary dates will be imputed based on nominal date. For example, a subject's first dose in ED is 18May2017, his/her ER day diary date will be 18May2017 and his/her Day 1 diary date will be 19May2017.

9. STATISTICAL METHODOLOGY AND STATISTICAL ANALYSES

9.1. Study Population and Demographics

Demographic and pretreatment patient characteristics, including disease parameters and comorbidities, will be summarized with descriptive statistics. The descriptive statistics will include sample size, mean, standard deviation, median, minimum, and maximum for continuous variables and number and percentages for discrete variables.

Baseline chemistry, CBC and urinalyses were performed on selected patients prior to amendment 4. Beginning with amendment 4, instituted in March, 2016, all patients were required to have chemistry and CBC performed; urinalysis remained optional. In addition beginning with amendment 4, pre- and 4 hr post-treatment ECGs were required of all patients.

Data for chemistry, CBC and urinalysis parameters are analyzed by treatment group, as described above. ECGs, which are performed pre- and post-treatment, are analyzed in greater detail, as described below.

9.2. Analyses of Primary Endpoint

Primary efficacy analysis will be based on the ITT population. The primary endpoint will be tested by Cochran Mantel Haenszel (CMH) test stratified by age. Common odds ratio and its 95% confidence interval will be provided. If the observed 2-sided p-value from the CMH test is

less than 0.05, statistical significance will be declared. Point estimates of the proportions for each treatment arm will be provided along with the corresponding 2-sided 95% confidence intervals. The point estimate of the difference of the proportions between treatment arms will also be provided along with corresponding 2-sided 95% confidence intervals.

For the above primary analysis, Patients who drop out of the study and patients who have unknown primary endpoint will be imputed as failures/non-responders, as stated in the handling of missing value section above.

As a sensitivity analysis, patients who drop out of the study and patients who have unknown primary endpoint will be imputed as responders. The primary analysis of CHM by age will be repeated.

One additional sensitivity analysis, the most conservative approach, will have following imputations:

- patients who drop out of the study and patients who have unknown primary endpoint in active arm will be imputed as failures/non-responders
- patients who drop out of the study and patients who have unknown primary endpoint in placebo arm will be imputed as responders

In addition, subgroup analyses by each age group (<18 , ≥ 18 years of age) will be conducted. For a given age group, unstratified CMH test will be performed. Furthermore, subgroup analyses by baseline nausea severity will also be conducted. None and mild severity will be combined as one group. For a given severity group, unstratified CMH test will be performed.

Primary analysis will also be performed on Subgroup Population 1 and Subgroup Population 2.

9.3. Efficacy Analyses for Secondary and Tertiary Endpoints

ITT population will be used for the analyses of all secondary and tertiary endpoints.

1) Analyses of Binary/Proportion Endpoint

Same statistical test as for the analyses of the primary endpoint, as stated in Section 9.2, will be used for analyzing other proportion endpoints.

2) Analyses of Time-to-Event Endpoints

Time to event endpoints will be compared between the treatment arms using stratified log-rank test adjusting the age stratification factor. The endpoints will also be summarized using the Kaplan-Meier method and displayed graphically when appropriate. Median event times and 2-sided 95% confidence interval for each median will be provided.

3) Analyses of Continuous Endpoints

Descriptive statistics, including the mean, standard deviation, median, minimum, and maximum values, will be provided for continuous endpoints.

4) Analyses of Ordinal Categorical Endpoints

The number and percentage of patients in each category will be provided for categorical endpoints. Bristol Stool Scale (BSS), added in the Protocol Amendment 3, is an 8 point ordinal categorical variable. Wilcoxon rank sum test will be used to compare the two treatment groups.

5) Concordance Assessment of Bristol Stool Scale and Stool consistency

Stool consistency, as recorded per original protocol, none/formed (normal)/soft/watery (diarrhea), is a 4 point ordinal categorical variable. Cross-tabulation of stool consistency and BSS among all the patients who have both assessments at a given time point will be created to evaluate the concordance of the two scales. Cohen's Weighted Kappa Coefficient and 95% confidence interval will be provided.

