#### 5.2.2 Observation while in emergency department

To start immediately after administration of study medication:

- Intake and output hourly:
  - all oral and parenteral intake

- urination: number of voidings
  - vomiting: number of episodes
  - stool output: number, consistency (per scale in original protocol and per Bristol Stool Scale, Appendix I)
- Vital signs at least hourly and just prior to discharge: temperature, blood pressure, pulse, respiratory rate
- Questioning regarding adverse events: hourly and just prior to discharge
- Assessments of nausea: on signing informed consent, just prior to first dose of study medication, hourly, just prior to discharge from emergency department. A 5-point Likert scale will be used:
  - 0 No nausea
  - 1 Mild nausea
  - 2 Moderate nausea
  - 3 Severe nausea
  - 4 Nausea as bad as can be

- 12-lead ECG 4±0.25 hours after initial dose of study medication (regardless of whether dose was repeated in ED). If patient leaves ED <4 hours after dosing, an ECG should still be obtained just prior to discharge.
- Brief physical examination of pertinent systems prior to discharge

If a patient vomits ≥30 minutes after taking the first dose of study medication, requires rescue antiemetic or parenteral hydration, he or she will be considered a treatment failure. The patient will be followed according to the schedule above for a total of 4 hours from the time of first administration of study medication or until discharged home, whichever comes first. After that, for patients still in the emergency department or hospital, the patient will be followed per standard protocol, according to the patient's condition.

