#### 7.4.4 Secondary Analyses

Additional analyses will be done comparing the following parameters between treatment groups:

- Proportion of patients who experience or require each of the components of treatment failure:
  - Vomiting
  - Rescue antiemetic therapy
  - Intravenous hydration
- Severity of nausea

- Incidence and severity of diarrhea
- Incidence and severity of other symptoms of gastroenteritis
- Time from first dose of study medication to discharge from ED, extended observation unit or hospital, whichever comes last
- Time to resumption of normal activities (work/school/household)
- Proportion of patients requiring hospitalization
- Proportion of patients returning to emergency department for gastrointestinal symptoms within 4 days of initial discharge

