1.2.2 Secondary Objectives

Comparison between ondansetron and placebo groups of

- Treatment success, as defined above, through 4 days following first dose of study medication
- Proportion of patients who experience each of the components of treatment failure:
 - Vomiting
 - Rescue antiemetic therapy
 - Intravenous hydration
- Severity of nausea
- Diarrhea as reported by
 - Bristol Stool Scale (BSS): number and distribution by grade of grade ≥ 5 stools daily throughout the study
 - Stool consistency, as recorded per original protocol, none/formed (normal)/soft/watery (diarrhea)
- Incidence and severity of other symptoms of gastroenteritis
- Time from first dose of study medication to discharge from ED, extended observation unit or hospital, whichever comes last
- Time to resumption of normal activities (work/school/household)
- Proportion of patients requiring hospitalization
- Proportion of patients returning to emergency department for gastrointestinal symptoms within 4 days of initial discharge
- Adverse events

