7. ENDPOINTS AND COVARIATES

7.1. Efficacy Endpoint(s)

- 1) Primary Efficacy Endpoint: the proportion of patients who fulfill all the following 3 criteria from 30 minutes after first administration of study medication until 24 hours after the first dose of study medication:
 - a. absence of vomiting
 - b. no use of rescue medication, and
 - c. no intravenous hydration

If all of the above three criteria are fulfilled, the patient is considered a treatment success for the primary analysis. If one or more of the above three criteria are not fulfilled, i.e., the patient either experiences vomiting, receives rescue medication or receives intravenous hydration from 30 minutes through 24 hours after the first dose of study medication, the patient is considered a treatment failure.

Based on the 2nd blinded dry run conducted on [REDACTED], there were 28 subjects who did not have all the information needed to determine per the algorithm used if they met the primary endpoint successfully. For 17 patients, all treated under amendment 1 or 2, in which the primary endpoint was treatment success on emergency department discharge, the reason for not having complete information was the lack of an ER day diary. For these patients, based on all follow up data available, no treatment failure events occurred. Therefore, these patients are considered treatment successes. Among the other eleven, data were reviewed and several queries issued. Based on this review, patients were assessed by the medical monitor to be treatment successes (n=4), failures (n=1) or unknown (n=6). The adjudicated primary endpoint outcomes will be used for the primary analyses.

2) Secondary and Tertiary Efficacy Endpoints:

- Treatment success, as defined above, through 4 days following first dose of study medication
- Proportion of patients who experience or require each of the components of treatment failure:
 - Vomiting
 - Rescue antiemetic therapy
 - Intravenous hydration
- Severity of nausea
- Incidence and severity of diarrhea
- Incidence and severity of other symptoms of gastroenteritis
- Time from first dose of study medication to discharge from ED, extended observation unit or hospital, whichever comes last
- Days to resumption of normal activities (work/school/household)
- Proportion of patients requiring hospitalization
- Proportion of patients returning to emergency department for gastrointestinal symptoms within 4 days of initial discharge

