7.3. Covariates

The analyses of the primary and secondary endpoints will be performed using the following randomization stratification factor as covariate:

- Age (<18, \geq 18 years of age)

Analyses of a given continue endpoint will also include its corresponding baseline as a covariate.

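### Does SAP 9.3 need a test of the number of loose stools, a defined value for the Bristol Stool Scale Wilcoxon test, and a category map for the kappa?

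*SAP*

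**What the plan says.** The SAP's secondary objectives (1.2.2) list, among the items to be compared between arms, the "number and distribution by grade of grade" 5 or higher stools on each study day. The endpoint lists that feed the analysis (Protocol 7.4.4 and SAP 7.1) word it more broadly: "Incidence and severity of diarrhea".

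SAP 9.3 assigns methods by type of variable:

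- Item 1: proportions get the age-stratified CMH test.
- Item 3: continuous endpoints get descriptive statistics only.
- Item 4: categorical endpoints are shown as numbers and percentages of patients per category, and the BSS "is an 8 point ordinal categorical variable. Wilcoxon rank sum test will be used to compare the two treatment groups".
- Item 5: the older stool consistency scale "is a 4 point ordinal categorical variable" (none, formed, soft, watery). It is cross-tabulated against the BSS in patients rated on both scales at the same time point, and Cohen's "Weighted Kappa Coefficient and 95% confidence interval will be provided".

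SAP 7.3 adds a general rule: "The analyses of the primary and secondary endpoints will be performed using the following randomization stratification factor as covariate", namely age under 18 or 18 and over.

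On data capture, Protocol 5.2.2 records each hour in the emergency department (ED) the "stool output: number, consistency (per scale in original protocol and per Bristol Stool Scale, Appendix I"). Protocol 5.2.3 has the diary describe each bowel movement after discharge.

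**The concern.** Four things look unfinished.

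1. **Count.** The objectives name a number of stools, but no item of 9.3 tests a number between arms.
2. **Ranked value.** A patient may have many rated stools in a day. The Wilcoxon test needs one value per patient, and none is defined. Appendix I has seven types, so the eighth point is also unexplained. For discharges at 8 pm or later, Protocol 4.5 carries only vomiting and adverse events from that evening into the diary, not stools.
3. **Age stratum.** Items 1 and 2 of 9.3 repeat it, and item 4 does not.
4. **Kappa.** Weighted kappa needs both ratings on the same categories. A 4-by-8 table has no diagonal, and neither map nor weights are given. The border between formed and soft is arguable, because Appendix I uses the word soft for both Type 4 and Type 5.

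At stake is whether a listed comparison goes untested, and whether a p-value and an agreement coefficient rest on choices made after the study was unblinded on June 3, 2017.

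**Working it through.** The plan states no sample size, power or expected value for stool data, so there is no figure to reproduce. The check sets the passages side by side and then uses assumed stool data to size each gap.

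**Ranked value.** Item 4 counts patients in each category and item 5 speaks of a given time point, so one value per patient per time point is implied. SAP 8 assigns diary pages to nominal dates (ED day, then Day 1 the next day), which settles most of the day question. The companion scale begins with none, and seven types plus none makes eight. What remains open is worst, median or some other grade.

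Illustration: 192 and 128 patients, mean 1.4 versus 2.0 stools per day, gamma-Poisson counts with shape 1.5, the same grade mix in both arms, 1000 simulated trials, unstratified Wilcoxon. Share with p < 0.05:

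| Value ranked | Share |
|---|---|
| Number of grade 5 or higher stools | 64% |
| Worst grade | 50% |
| Median grade | 30% |
| Every stool as its own observation | 5.5% |

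The last row is ruled out by item 4's wording, since it counts stools and not patients. The contrast also depends on the assumed effect. If half of Type 7 stools become Type 5 and the number is unchanged, at 192/128 the count test rejects in 5 to 7% of trials and the worst-grade Wilcoxon in 51 to 74%. Neither test dominates.

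**Age stratum.** SAP 7.3 already applies it to secondary endpoints, and not repeating a general rule contradicts nothing. On assumed data with under-18 stool rates 1.5 to 3 times the adult rate, stratifying changes the power of the worst-grade test by -1 to +3 points.

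**Kappa.** Assumed ratings, 10% of them moved one step, generated under the first map:

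| Map of BSS to none / formed / soft / watery | Linear | Quadratic |
|---|---|---|
| none / 1-4 / 5-6 / 7 | 0.93 | 0.96 |
| none / 1-4 / 5 / 6-7 | 0.83 | 0.91 |
| none / 1-3 / 4-5 / 6-7 | 0.73 | 0.85 |

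The map moves linear kappa by 0.93 - 0.83 = 0.10 to 0.93 - 0.73 = 0.20. Unmapped codes in an 8-by-8 table would give only 0.24 to 0.31 (linear) even with perfectly ordered agreement, and the planned cross-tabulation would expose that at once.

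**Adding a count test.** The obvious form averages ED and diary counts over the days with data. Protocol 5.2.3 gives diary cards to patients who are successes in the ED and plans a single call at 72-96 hours for failures. Protocol 7.1 expects failure in 20% on RHB-102 and 40% on placebo. If every failure lacked diary data, that is 0.20 x 192 = 38 patients against 0.40 x 128 = 51.

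Suppose the drug does nothing to stools, with a mean of 2 loose stools per day at the start, and take the ED record plus four diary days as five days.

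- *Flat rate, ED record covering a quarter of a day.* Complete patient: (0.5 + 4 x 2)/5 = 1.7. Failure: 0.5. RHB-102: 0.8 x 1.7 + 0.2 x 0.5 = 1.46. Placebo: 0.6 x 1.7 + 0.4 x 0.5 = 1.22. The drug looks worse.
- *Rate halving daily, ED record covering a full day.* Complete patient: (2 + 1 + 0.5 + 0.25 + 0.125)/5 = 0.775. Failure: 2. RHB-102: 0.8 x 0.775 + 0.2 x 2 = 1.02. Placebo: 0.6 x 0.775 + 0.4 x 2 = 1.265. The drug looks better.

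Simulation at 192/128 used an ED record of 0.25 to 1 day, a flat, mildly falling or halving rate, 50% or 100% of failures without diary data, an age-stratified (van Elteren) test and 2000 trials per setting. It rejects the true null in 5 to 46% of trials at nominal 5%. A second run agreed within simulation error.

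**The case for a change.** The best case for a change is that the gaps are real and cheap to close. No text in SAP 9.3 names the ranked grade, the map or the weights, and the tables above show that these choices alter results. A count is named in the objectives, and counts and grades answer different questions. SAP 7.3 also speaks of adjusting continuous endpoints for baseline, which sits oddly with the descriptive-only rule in 9.3 item 3.

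Much of this stands as an observation about drafting, but less of it supports a change.

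- The objectives list that speaks of comparison also contains adverse events, which get summary tables only (SAP 9.4). A place on that list does not promise a hypothesis test. The endpoint lists ask for incidence and severity, which the CMH and Wilcoxon tests can serve.
- The claim that choices were left until after unblinding cannot be established. SAP 7.1 refers to programmed derivations ("Based on the 2nd blinded dry run conducted on" a date before unblinding), and the Supplemental SAP cites a numbered output table, so programs or shells existed. The SAP describes the dry run only for the primary endpoint, so whether it covered stools is unknown either way.
- A count test written now would be specified after unblinding and could only be exploratory. In its simple form it is biased by outcome-dependent follow-up. Patients who fail after discharge already hold a diary card, so complete loss among failures is the extreme case, but half loss is simulated too.

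**Conclusion.** No change to the plan is called for. The missing ranked value, eighth level, map and weights are definitions that an analyst must supply to run the procedures. The wording on patients per category, the time points, the none level of the companion scale and the age rule in SAP 7.3 lead to sensible choices. Those choices will be visible in the output: the table has to name the grade summarised, and the cross-tabulation is valid without any map.

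The consequence is confined to one secondary endpoint and a scale check that carries no treatment inference. SAP 5.2 attaches its decision rule to the primary hypothesis, and that analysis is not affected. Describing the stool counts without testing them is a fair reading of 9.3 item 3. Given diary follow-up that depends on treatment failure, it is safer than a test of averages over available days.

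This rests on assumed stool distributions, since the documents give none, and on the planned sizes of 192 and 128. The number of patients with BSS data is smaller and not stated, because the scale entered with Amendment 3. Fewer patients would lower every power figure without altering the reasoning.

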### 1.4 Study Rationale

As noted above, ondansetron has been studied in acute gastroenteritis against placebo in seven clinical trials and against other agents in two studies. While often used clinically, its activity in adults and adolescents with acute gastroenteritis has not been demonstrated. Thus, a prospective randomized study of ondansetron in a major patient population will provide clear evidence of the efficacy of the drug, or lack thereof, in this population.

The study will of necessity enroll only those patients who are likely to tolerate oral medications. Patients with vomiting at a frequency which make it difficult for them to hold down a pill for half an hour are not appropriate for this study and will be excluded. However, for the large population of patients with moderate gastroenteritis, treatment of the disease without intravenous is clearly preferable. In addition to being easier and more comfortable even in an emergency department setting, it will allow treatment of patients outside the emergency room, providing both patient convenience and economic benefits as compared to parenteral treatments in an emergency department.

Use of a placebo control allows demonstration of activity with a reasonable sample size. Ondansetron has a very benign safety profile; one of the side effects of ondansetron, constipation, is actually a therapeutic benefit in the intended indication. In contrast, adverse events are more common with phenothiazines and metoclopramide, and they may be severe. These include dystonia and akathesia. Therefore, use of a placebo control in patients with moderate gastroenteritis may spare some patients toxicity in a situation where not all patients require pharmacologic intervention. Those patients who do require medication will promptly receive an active rescue intervention.

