## 7. Data Analysis and Statistical Considerations

### 7.1 Sample Size Considerations

The primary endpoint is a composite of the following three parameters from 30 minutes until 24 hours after the first dose of study medication:

- absence of vomiting
- no use of rescue medication, and
- no intravenous hydration

If all of the above three criteria are fulfilled, the patient is considered a treatment success for the primary analysis. If one or more of the above three criteria are not fulfilled, i.e., the patient either experiences vomiting, receives rescue medication or receives intravenous hydration from 30 minutes through 24 hours after the first dose of study medication, the patient is considered a treatment failure.

It is expected that approximately 40% of the placebo group will fail treatment during the 24 hours after initial dosing and that RHB-102 will reduce the incidence of treatment failure by approximately 50%, i.e., to an incidence of 20% in the active treatment group. Patients will be stratified by age (<18,  $\geq$ 18 years of age) and randomized 60:40 to active versus placebo. To demonstrate a statistically significant decrease in the incidence of vomiting with a 2-tailed p-value=0.01 and power=90%, 320 patients will be entered into the study, 192 randomized to RHB-102 and 128 to placebo.

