## Appendix I. Bristol Stool Scale

Type 1	 Separate hard lumps, like nuts (hard to pass)
Type 2	 Sausage-shaped but lumpy
Type 3	 Like a sausage but with cracks on its surface
Type 4	 Like a sausage or snake, smooth and soft
Type 5	 Soft blobs with clear-cut edges (passed easily)
Type 6	 Fluffy pieces with ragged edges, a mushy stool
Type 7	 Watery, no solid pieces. Entirely liquid

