5. HYPOTHESES AND DECISION RULES

5.1. Statistical Hypotheses

The primary objective for the study is to test for superiority of RHB-102 vs placebo for the proportion of the primary endpoint.

The null hypothesis is that the odds ratio between the two treatment groups is one, i.e. there is no treatment difference in the proportions of the primary endpoint. Cochran Mantel Haenszel (CMH) test stratified by age will be used to test the null hypothesis. The hypothesis will be tested at an overall level of 0.05 (2-sided).

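### The Wilcoxon test in SAP 9.3(4) ranks the whole Bristol scale, so shifts below grade 5 can raise the chance of a significant result favouring RHB-102 with no change in loose stools

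*SAP*

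**What the plan says.** SAP 9.3, item 4, states that the Bristol scale "is an 8 point ordinal categorical variable. Wilcoxon rank sum test will be used to compare the two treatment groups". No cut at grade 5 is given. A test confined to grades 5 and above would have three grades, or four with a level for no loose stool, so eight points indicates the whole scale.

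The objective in SAP 1.2.2 is narrower: "Bristol Stool Scale (BSS): number and distribution by grade of grade ≥ 5 stools daily throughout the study". Protocol 2.2 and the synopsis carry the same restriction. SAP 7.1 lists the endpoint as "Incidence and severity of diarrhea" without repeating the grade threshold.

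Protocol Appendix I lists seven types. Type 1 is "Separate hard lumps, like nuts (hard to pass") and type 7 is "Watery, no solid pieces. Entirely liquid". The eighth level is not defined; no stool is the natural guess.

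Protocol 1.4 says that "one of the side effects of ondansetron, constipation, is actually a therapeutic benefit in the intended indication".

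**The concern.** A rank sum test counts every step down the scale in the same direction. A patient who goes from smooth stool (type 4) to hard lumps (type 1) contributes to the comparison just as a patient whose stool becomes less liquid does. The objective concerns only grade 5 and above, so movement below that grade is outside it but still enters the p-value.

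The direction of this movement is foreseeable, because the protocol itself names constipation as an effect of the drug. At stake is how a significant Bristol result would be read. It could be taken as less diarrhea when part of the signal, or in the limiting case all of it, came from patients who had no loose stool under either treatment.

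**Working it through.** **The plan's own figure.** The documents give no power or effect size for the Bristol test. The only design figure is for the primary endpoint: "with a 2-tailed p-value=0.01 and power=90%, 320 patients will be entered into the study, 192 randomized to RHB-102 and 128 to placebo". With failure rates of 0.40 and 0.20 and ratio r = 1.5, the average rate is (0.40 + 1.5 × 0.20)/2.5 = 0.28. Then

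n(placebo) = [2.576 √((1 + 1/1.5) × 0.28 × 0.72) + 1.282 √(0.24 + 0.16/1.5)]² / 0.20² = (1.493 + 0.755)² / 0.04 ≈ 126.3,

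which rounds up to 127 and gives 191 on RHB-102, 318 in total against 320 stated. The figure reproduces. Here 192/128 serves only as an upper bound, because Bristol collection began with Amendment 3. The actual number is not given, and 96/64 is taken as an assumed lower case.

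**Assumed inputs.**
- Placebo shares for none and types 1 to 7: 0.15, 0.02, 0.03, 0.15, 0.25, 0.12, 0.14, 0.14 (loose, types 5–7: 0.40).
- RHB-102 has the same shares for types 5–7; only patients in types 3–4 move.
- One independent value per patient, and no stool ranked lowest.
- Two-sided 0.05. This level is stated for the primary hypothesis ("The hypothesis will be tested at an overall level of 0.05 (2-sided")) and assumed for the Bristol test.

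**Effect on the rank comparison.** For each level let s = P(placebo value higher) − P(placebo value lower):
- none: 0.85
- type 1: 0.83 − 0.15 = 0.68
- type 2: 0.80 − 0.17 = 0.63
- type 3: 0.65 − 0.20 = 0.45
- type 4: 0.40 − 0.35 = 0.05

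Let D = P(active lower) − P(active higher), which is 0 when the arms are equal. A 20-point shift taken proportionally from types 3 and 4 removes 0.075 × 0.45 + 0.125 × 0.05 = 0.040.
- Moved to types 1–2: it adds 0.08 × 0.68 + 0.12 × 0.63 = 0.130, so D = 0.090.
- Moved to none: it adds 0.20 × 0.85 = 0.170, so D = 0.130.

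D scales with the shift: 0.045 and 0.065 for 10 points, 0.0225 and 0.0325 for 5 points.

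**Rejection rate.** SE(D) = 2 √[(N+1)(1 − Στ³)/(12mn)], where τ are the pooled level shares. For the 20-point shift, Στ³ is 0.0185 (to types 1–2) or 0.0335 (to none). SE is then 0.0654 or 0.0649 at 192/128, and 0.0926 or 0.0919 at 96/64. Power is approximately Φ(D/SE − 1.96) + Φ(−D/SE − 1.96). For example, 0.090/0.0654 = 1.38 gives Φ(−0.58) = 28%.

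| Shift (points) | To types 1–2, 192/128 | To types 1–2, 96/64 | To none, 192/128 | To none, 96/64 |
|---|---|---|---|---|
| 5 | 6% | 6% | 8% | 6% |
| 10 | 10–11% | 8% | 17% | 11% |
| 20 | 28% | 16% | 52% | 29% |

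Simulation agrees: for 20 points, 29%, 16%, 51% and 28% in the same column order. Repeat runs at 192/128 ranged over 26–29% and 51–54%. At the larger shifts almost all rejections favour RHB-102.

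**Dependence on the stool mix.** In a second set of assumed mixes, half of types 3–4 moved to types 1–2, or half of types 1–4 moved to none. The share of simulated trials significant in favour of RHB-102 (nominal 2.5% in that direction) was:

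| Loose stools in both arms | To types 1–2, 192/128 | To types 1–2, 96/64 | To none, 192/128 | To none, 96/64 |
|---|---|---|---|---|
| 30% | 58% | 31% | 87% | 58% |
| 50% | 19% | 11% | 33% | 19% |
| 70% | 5% | 4% | 8% | 6% |

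**With levels below 5 tied.** Both arms then have the same share below 5 and the same shares in 5, 6 and 7, so D = 0 exactly whatever moves below 5. Simulated rejection was 4–6% throughout.

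**The case against.** The SAP calls the scale ordinal, not a severity order, and leaves the value ranked undefined (each stool, the loosest of the day, or one per patient). If the loosest stool of the day is ranked, a patient scores type 1–2 only when every stool that day was hard, and the modelled shifts become much harder to produce. A 20-point shift means that half of the assumed type 3–4 patients become constipated; no document supports that size. Follow-up data are also thinner than 192/128. Beyond the Amendment 3 start, Protocol 5.2.3 gives treatment failures a single later call and describes the diary for successes. All of this stands, and it limits the size.

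Other planned outputs would also reveal such a shift. SAP 9.3(4) gives counts and percentages by category. The second stool scale (none, formed, soft, watery) has no hard-stool end, so a move from types 3–4 to types 1–2 should not register there, although a move to none could. Diarrhea incidence, if analysed as a proportion, falls under the CMH test of 9.3(1) and would not respond to shifts below loose stool. Adverse events are tabulated by preferred term. These help a careful reader, but none of them corrects the Wilcoxon p-value.

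The sponsor may add that the protocol counts constipation as a benefit. So far as that means fewer loose stools, the grade 5+ measure captures it. Harder stool in patients without diarrhea is outside the stated objective.

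**Conclusion.** The point holds as a mismatch between test and objective: the planned test lets movement below grade 5 into the diarrhea comparison, in a direction the protocol leads one to expect. Under the 40% loose mix the inflation is modest for shifts of 5–10 points (about 6–17%). It is material for a 20-point shift: 16–29% to types 1–2, or 28–51% to no stool if that is the eighth level and ranked lowest. It shrinks towards nominal when most stools are loose. The stool mix, the shifts, the Bristol sample and one value per patient are assumptions. The move from types 3–4 to types 1–2 shows the fault without relying on the eighth level.

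A reader might infer that a diarrhea benefit would rest purely on constipation. The documents do not support that: nothing in them shows the size of any constipating shift, a true reduction in loose stools would also move the test, and the other planned tables would expose a shift among hard and formed stools. Nor does the point reach the trial's main conclusion. This is one of many secondary and tertiary endpoints, and the claim rule in SAP 5.2 is written for the primary hypothesis. The correction is worth making because it is cheap and matches what the objective already says.

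**What to change.** - For the diarrhea comparison, tie none and types 1–4 as one level and rank 0, 5, 6, 7. State the value ranked per patient, how repeated days are handled, and what the eighth level is.
- Compare the number of grade 5+ stools alongside it, since the objective asks for number as well as distribution.
- Read types 1–2 by arm from the category percentages already planned; no new table is needed.
- The supplemental SAP records that SAP 4.0 was signed on June 1, 2017 and the study unblinded on June 3, 2017. Report this as a labelled supplementary analysis beside the planned Wilcoxon test, not as a replacement, and rest any diarrhea claim on the grade 5+ result.

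The cost is one recode and one count comparison on data already collected. The small downside is that the diarrhea result may look less favourable.
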